7.4 Statistical Methods

The primary analysis will be a Site x Time ANOVA on the Hamilton Depression rating scale comparing pretreatment to symptoms immediately following each round of stimulation. This test will be augmented by a Site x Time ANOVA for pre-treatment compared with the 6 month timepoint to explore the degree of maintenance of treatment benefits.

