Study Duration	8 months (Screening, 9 weeks of treatment visits with a 3-week break, and 6 months of phone/survey follow-up visits)		
Study Center(s)Center for Neuromodulation in Depression and Stress University of Pennsylvania School of Medicine Department of Psychiatry			
Objectives	We aim to compare the efficacy of rTMS treatment to two sub-regions of the Dorsolateral Prefrontal Cortex (DLPFC). We will examine the standard positioning of TMS used in clinical settings compared with TMS using MRI to guide the precise location of stimulation. We hypothesize that fMRI-guided TMS will produce greater benefit to patients with MDD/PTSD than the standard targeting method for TMS.		
Number of Subjects	N=80; n=40		
Main Inclusion and Exclusion Criteria	18-60; inclusive; no TMS contraindications; no medication use that substantially reduces seizure threshold or interferes with fMRI recordings; PTSD diagnosis or trauma induced MDD (SCID interview) and elevated depression (PHQ \ge 10).		
Investigational Product (drug, biologic, device, etc.)	MagVenture devices for rTMS administration include: -MagPro X100* magnetic stimulator -Cool-B65 Butterfly Coil		
Duration of administration (if applicable)	2 sets of 10 consecutive weekdays (at minimum 4 sessions per week with a total of 10 overall sessions per set)		
Reference therapy	N/A		
Statistical Methodology	Clinical outcome will be evaluated on symptom scales in a TMS target x Time ANOVA. Similarly, rate of change (slope) x TMS Target will indicate how rapidly each treatment improves symptoms.		

Safety Evaluations	TMS protocols will be administered by specially-trained staff from the Center or Neuromodulation in Depression and Stress the University of Pennsylvania Department of Psychiatry. All TMS staff will be trained by the PI ([name].) and the Center Director ([name].).		
Data and Safety Monitoring Plan	The PI will be responsible for monitoring the data quality and the ongoing safety of subjects.		

CONFIDENTIAL

BACKGROUND AND STUDY RATIONALE

Introduction

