1.1 Background and Relevant Literature

The subgenual Anterior Cingulate Cortex (sgACC) has been well established as a brain area sensitive to negative mood inductions and implicated in neural abnormalities associated with affective and stress disorders. It is therefore one of the primary targets for deep brain stimulation (DBS) treatment of MDD using surgically implanted DBS devices. Recent posthoc imaging studies of patients who have undergone TMS treatment for depression suggest that treatment outcomes tended to be better when patients were by chance stimulated in an area of lateral prefrontal cortex that had high levels of functional connectivity with sqACC. Based on this finding and on our own interleaved TMS/fMRI probe data, we contend that targeting delivery of TMS to the brain surface non-invasively as indicated by sqACC resting functional connectivity may be especially effective in downregulating sqACC and thereby producing superior clinical outcomes. We have used TMS/fMRI to better understand causal communication among circuits typically examined with resting fMRI alone (Chen et al., 2013). Our recent work suggests that there are specific sites that, when stimulated, influence subcortical brain areas implicated in affective disorders such as the sgACC. Previously, we targeted TMS based on brain atlases mapped onto individual brain surfaces. This proposal will utilize more individualized targeting from participants own resting connectivity data to guide stimulation that we show is especially effective in influencing downstream brain areas of interest. We will focus on a target region that our data suggest is particularly effective at influencing the sqACC. As an alternative brain target, we will also test the efficacy of the dorsolateral prefrontal cortex as a target given its precedence as an FDA-approved stimulation site for remediating depressive symptoms. To increase generalizability to other disorders and to patients with comorbid anxiety and depression (the typical clinical profile), we will recruit patients who are diagnosed with PTSD or trauma induced MDD and who have elevated depression (PHQ). We will recruit them, scan them in the MRI to get anatomical and resting fMRI data to guide TMS, then will invite them to participate in two rounds of two-week TMS treatment to each site (order counterbalanced) with approximately one month between treatments. We will monitor depressive (MADRS), PTSD (PCL Checklist), and quality of life (WHOQOL) measures before, acutely after, and every month for 6 months following TMS treatments to evaluate the effectiveness of each site in mitigating symptoms or improving functioning. A typical, FDA-approved clinical application of TMS involves long trains of repetitive TMS applied for approximately 40 minutes, 5 days/week, over 2-6 weeks, for a total of 10-30 TMS visits. The present study utilizes the same FDA-approved devices (Magventure Cool-Coil B65, MagVenture X100 Stimulator) to administer treatment. We will be modifying the FDA-approved protocol to stimulate similarly to a well-replicated protocol, theta-burst stimulation (Huang et al., 2005). We have attached several additional examples of prior studies which have safely utilized TMS outside of its FDAapproved protocol, even in heightened doses. For instance, in prior studies subjects have received FDAapproved 3000 rTMS pulses, but done bilaterally instead of unilaterally (6000 total stimulations) every weekday over 4-6 weeks (see Bakker et al., 2015). Similarly, subjects have received 3600 rTMS pulses every weekday over 10 days (see Chistyakov et al., 2015), or 3000 rTMS pulses every weekday over 6 weeks (see O'Reardon et al., 2007). Another study applied the FDA-approved protocol in more than a double-dose, with 6800 stimulations to 1 site every weekday over 7 weeks average participation (Hadley et al., 2013). The present study utilizes fewer stimulations than the FDA-approved protocol, with each visit including a maximum of 3700 pulses. For additional information, please see Anderson et al., 2006 for demonstrations of the safety of repeated exposure to TMS. Likewise, please see Wagner et al., 2007 and Parkin et al., 2015 for reviews of the importance of TMS research and how our proposed studies fit in the present and growing body of literature.

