3.2 Study Endpoints

3.2.1 Primary Study Endpoints

The primary endpoint will be clinical improvement due to TMS at either of the two target regions. The study will focus on a target region of the fMRI-guided target and the standard DLPFC target, which is an FDA-approved rTMS treatment site. TMS-induced changes in brain activity are likely different for these two stimulation sites, despite their proximity. The aim of this study is to establish if using targets defined by resting connectivity in patients can be more effective at treating MDD/PTSD compared with standard targets.

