6.5 Other Evaluations, Measures

During the course of the study, patients' symptoms will be evaluated in order to determine changes in symptoms across the study. Symptom scales are detailed below in the "Efficacy Evaluations" section.

6.6 *Efficacy Evaluations*

The following clinical assessments will be utilized at baseline, after the first 2-week period of TMS treatment, during the TMS treatment 3 week break, and after the second 2-week period of TMS treatment (the end of the study) to evaluate the efficacy of the TMS interventions in improving clinical symptoms:

- Patient Health Questionnaire (PHQ-9)
- PTSD Checklist for DSM-5 (PCL-5)
- Montgomery-Asberg Depression Scale (MADRS)
- Columbia Suicide Severity Rating Scale (CSSRS)
- Positive and Negative Affect Schedules (PANAS 20 item)
- World Health Organization Quality of Life (WHOQOL-BREF)
- Snaith-Hamilton Pleasure Scale (SHAPS)

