7.4.3 Interim Analysis

After the first 12 participants are run for each protocol, the study team will evaluate the overall rate of change in symptoms. If less than one quarter of participants experience at least a 25% reduction in Hamilton Depression scores, the team will consider a change in stimulation protocol or target. Safety and tolerability will also be assessed at this interval and if the team decides that the procedures are safe and appropriate, enrollment will continue up to 60 participants.

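### The primary analysis and the interim efficacy criterion use the Hamilton Depression scale, which is not among the assessments the protocol lists

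*Combined protocol and SAP*

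**What the plan says.** Section 7.4 fixes the outcome of the main test: "The primary analysis will be a Site x Time ANOVA on the Hamilton Depression rating scale". The comparison is of pre-treatment scores with scores directly after each round of stimulation. A further ANOVA, described as exploratory, compares pre-treatment with 6 months.

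Section 7.4.3 uses the same scale for the interim look: "If less than one quarter of participants experience at least a 25% reduction in Hamilton Depression scores", the team will consider changing the stimulation protocol or target. Section 7.3 takes its effect size (Hedges' g of 1.225) from published percentage improvement on the Hamilton Depression scale.

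On data collection, 6.5 says "Symptom scales are detailed below in the" efficacy section, which is 6.6. Section 6.6 lists seven instruments: PHQ-9, PCL-5, MADRS, CSSRS, PANAS, WHOQOL-BREF and SHAPS. It gives their times as baseline, after the first round, during the break, and after the second round. Section 1.1 names the measures by domain: "We will monitor depressive (MADRS), PTSD (PCL Checklist), and quality of life (WHOQOL) measures before, acutely after", and then monthly for 6 months.

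Elsewhere the outcome is described without an instrument. The Study Summary says "Clinical outcome will be evaluated on symptom scales in a TMS target x Time ANOVA". Section 3.2.1 says "The primary endpoint will be clinical improvement due to TMS at either of the two target regions". Sections 7.1 and 7.4.2 are equally general, as are 3.2.2 and 7.2 for the secondary endpoint.

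**The concern.** Section 7.4 is the only place where the primary analysis is tied to a named instrument, and that instrument is missing from the list to which the protocol sends the reader for symptom scales. Staff who collect exactly what 6.6 lists will hold no Hamilton scores. The stated primary analysis could not then be run, and the interim efficacy criterion could not be evaluated.

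The loss would be permanent for anyone already treated, because a pre-treatment rating that was not taken cannot be obtained later. A replacement outcome would have to be named, and the general wording of 3.2.1, 7.1 and 7.4.2 does not say which.

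**Working it through.** This is a consistency check, so the main work is to set the sections side by side. The one related figure in the plan is reproduced first, to show that it is not the source of the problem.

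**The plan's own figure.** Section 7.3 gives g = 1.225, power 0.80 and p 0.05 (sidedness not stated), and a minimum of 6 patients for a change in symptoms. For a within-patient change, n = ((z for alpha + z for power) / g)². With two-sided 0.05 this is ((1.960 + 0.842) / 1.225)² = (2.287)² = 5.23, which rounds up to 6. A one-sided exact t calculation also gives 6 (power 0.822); a two-sided exact t calculation gives 8 (power 0.843). The stated 6 therefore reproduces as a within-patient calculation. It matters here only because its input is a Hamilton effect size.

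**Where the Hamilton Depression scale appears.**

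- 7.3: source of the effect size.
- 7.4: outcome of the primary analysis.
- 7.4.3: outcome of the interim efficacy criterion.

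In none of these is it described as an assessment to be administered.

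**Where assessments are specified.**

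- 6.6, to which 6.5 points: seven instruments, of which 0 is the Hamilton Depression scale. SHAPS carries the name Hamilton but is a pleasure scale. Two of the seven are depression scales, PHQ-9 and MADRS.
- Schedule table in section 6: a single row for clinical assessments, marked in every column, with no instruments named.
- 6.1: a structured diagnostic interview and the PHQ-9 for eligibility.
- 6.2.1 to 6.2.5: clinical assessments in general terms. The tasks named at baseline are neurocognitive.
- 1.1: MADRS for depression, PCL for PTSD, WHOQOL for quality of life.

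**What each analysis needs against what is listed.**

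- The 7.4 primary ANOVA needs Hamilton scores before treatment and after each round. Listed: none. MADRS is listed at baseline and after each round.
- The 7.4.3 criterion needs each participant's percentage reduction in Hamilton score. Listed: none.
- The 7.4 exploratory 6-month ANOVA needs Hamilton scores at baseline and 6 months. Listed: none. MADRS is stated monthly for 6 months in 1.1.

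**Which section is in error.** Section 1.1 and the 6.6 list point to MADRS. The repeated use of Hamilton in 7.3, 7.4 and 7.4.3 makes an omission from 6.6 equally possible. Nothing in the text decides between the two.

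**The case against.** The strongest reply is that 6.6 does not call itself exhaustive. The Hamilton scale recurs in three parts of section 7, so it may well be given under the general heading of clinical assessments. This stands to the extent that not listed must not be read as not collected. It does not remove the mismatch: 6.5 makes 6.6 the place where the symptom scales are set out, and no other section schedules a Hamilton rating.

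Three stronger readings are tempting, and the documents do not support them.

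- A reader might infer that the plan names competing primary outcomes. It does not. The Study Summary, 3.2.1, 7.1 and 7.4.2 are general and name no rival scale; 7.4 names exactly one. The conflict is between the scale analysed and the scales listed.
- A reader might infer that the false-positive rate is inflated by picking between PHQ-9 and MADRS once results are known. No section proposes such a choice. PHQ-9 serves as the eligibility scale, and 1.1 names only MADRS as the depression measure.
- A reader might infer that follow-up is also missing, because the times in 6.6 stop at "after the second 2-week period of TMS treatment (the end of the study"). But 6.2.5 and the schedule table place clinical assessments at the follow-up visits, 1.1 states MADRS monthly for 6 months, and the 6-month ANOVA is exploratory. The gap is one of wording in 6.6, not of planned data collection.

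The interim criterion is also non-binding, since the team only undertakes to consider a change, and the interim safety review does not depend on the scale.

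**Conclusion.** The mismatch is real and lies in intact text. The scale named for the primary analysis and for the interim efficacy criterion matches 0 of the 7 instruments in 6.6, and no other section schedules it. As written, neither can be computed from the listed assessments, so this needs correcting before outcome data are examined.

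The conclusion rests on reading 6.6 as the list of symptom scales, as 6.5 directs. It does not assume that the Hamilton scale is never given, nor that MADRS was intended. No numerical effect on error rate or power is claimed.

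**What to change.** Before outcome data are examined, name one collected depression scale as the primary outcome and reconcile 6.6 with 7.4 and 7.4.3. Use the same name in 3.2.1, 7.1 and 7.4.2, and for the clinical improvement or change on which the secondary endpoint in 3.2.2 and 7.2 depends. Either of two routes would do.

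(a) Use MADRS, which 6.6 lists at baseline and after each round and 1.1 lists monthly for 6 months. State in 7.3 that the 1.225 effect size comes from a different scale. Have the sponsor confirm that the 25% threshold in 7.4.3, written for Hamilton scores, still applies on MADRS.

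(b) If the Hamilton scale is in fact administered, add it to 6.6 and to the schedule at baseline, after each round and at 6 months.

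The other scales need no new label: 3.2.2 and 7.2 define a single secondary endpoint, and relabelling the rest as secondary would conflict with it.

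The cost is wording only if the chosen scale is already collected at these times. The drawback of (a) is an effect size borrowed from another scale. The drawback of (b), if the scale is not already given, is extra rater and patient time at each of those visits. Enrolment status matters too. The references to a September 2019 modification in 4.3 and to 2020 IRB discussions in 3.1.1 suggest, without proving, that the trial was under way. If it was, Hamilton baselines not taken cannot be recovered, and a change of primary scale should be documented as an amendment made before outcome data are examined.

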3.1 General Design

TMS will be administered to either the fMRI-guided target or DLPFC in a randomized, single-blind design. 40 patients diagnosed with Post-Traumatic Stress Disorder (PTSD) or trauma induced Major Depressive Disorder (MDD) and symptoms of depression, as determined by meeting the DSM criteria for PTSD or MDD as a primary diagnosis and scoring ≥10 on the PHQ-9, will be recruited for this study. They will be otherwise healthy adults, aged 18-60, with PTSD or trauma induced MDD as primary diagnosis and without current diagnoses of significant, problematic substance use disorders or with present or past diagnoses of psychosis or bipolar illness. All subjects will receive active TMS, so there is no placebo or sham condition. However, the patients will be blinded as to whether their site of stimulation is based on the clinical standardized targeting method or our novel fMRI-guided targeting method. TMS is administered to one of these two sites over a two-week period, and then TMS will be administered to the other site over a subsequent two-week period following a three week wash out period. All subjects will receive TMS to both sites as a part of the study, but the order is randomized and counterbalanced. All participants will be recruited through the community via study advertisements and through the University of Pennsylvania and the VA. Subjects can express interest by contacting the study staff; in most cases, this will serve as the primary method for acquiring contact information. Physician referrals and the use of the Penn Data Analytics Center will also be incorporated as recruitment methods. Section 4.3 further elucidates all recruitment methods. Prior to any study visits, all subjects will be screened in a telephone interview with a trained member of the study staff or via a self-report screening survey. The first study session will consist of a consenting and extended screening visit. The information collected in this initial visit will determine if the subject meets all inclusion criteria. We will also demonstrate TMS to ensure the subject is comfortable with all study procedures. At the second study session, participants will undergo an MRI procedure for 60 minutes. This will be used to generate the TMS targets for the study. Subjects will then return every weekday (5 days per week, minimum of 4 days per week) over two weeks to receive the TMS treatment (10 sessions). These visits will last approximately 60 minutes each. The daily administration of TMS is a necessary component of the study, as it is consistent with the standard operating procedure for FDAapproved clinical TMS. During the 2 weeks of TMS treatment, subjects will undergo the many of the same clinical assessments used during the screening and baseline visits, in order to examine changes in symptoms. Subjects will then spend 3 weeks away from the study team; during the break, there will be two phone/survey visits used as a safety assessment. After this break, subjects will then return every weekday (5 days per week, minimum of 4 days per week) over two weeks to receive the TMS treatment (10 sessions) to the other site examined in the study. Upon completion of the study, scheduled phone and survey visits will take place every 4 weeks (+/-7 days) over the subsequent 6-month period to monitor continued stability of clinical improvement and/or remaining clinical symptoms. Overall, this study consists of 1 consent/screening visit, 1 MRI scan, 20 total visits for TMS treatment, and 8 phone visits.

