6.7 Safety Evaluations

Only individuals trained by the Principle Investigator ([name].) and Center Director ([name].) will dispense TMS. The licensed physician ([name] or a suitable medically trained stand-in) will closely supervise any medical instability in patients and will specifically be responsible for training and overseeing syncope and seizure management which are not expected given our screening process but are the two primary health risks with TMS treatment.

[name], a board certified physician, will review all questionable screens for MRI and TMS safety and will be physically present (or a reasonable medically trained stand-in) for every TMS session conducted on any participant who indicates greater than minimal risk for experiencing syncope or a seizure in response to TMS.

Only research personnel will have keys and access to the TMS devices.

7 Statistical Plan

All recruitment will be conducted through the University of Pennsylvania, the Veterans Administration Medical Center, and surrounding community to find 80 patients with PTSD or trauma induced MDD and depressive symptoms. It is anticipated that a large portion of individuals will screen fail, withdrawal from participation or have unusable data. Therefore, 80 individuals will be consented/enrolled in this study, to ensure that there are 40 patients who complete the full protocol with usable data. This sample should provide us with adequate data to compare treatment sites relative to one another, since all patients will receive the standard targeting for TMS and also fMRI-guided TMS.

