7.4.1 Baseline Data

After 10 participants are randomly assigned to each stimulation order, an analysis of demographic data (age, education, gender, symptom severity) will address any initial differences in baseline characteristics of the two samples. If there is a systematic difference, randomization will be temporarily suspended to assign patients to one or other of the two groups in order to re-balance the initial baseline characteristics of the two groups. [Independent samples t-tests for continuous variables and Chi-square for categorical variables]

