7.4.2 Efficacy Analysis

Efficacy analyses will focus on comparisons between clinical symptoms at baseline, after the first 2-week treatment period, and at the end of the second 2-week treatment period. As noted above, the primary endpoint of this study will be a comparison focusing on clinical improvement due to TMS performed at either the standard brain target or the fMRI-guided brain target.

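### Section 7.4 leaves Site, the coding of Time and the site contrast undefined for a two-period crossover; if Time is collapsed to before/after, the primary test has no period term

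*Combined protocol and SAP*

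**What the plan says.** The design is a two-period crossover. Section 3.1 gives every patient both targets in randomised, counterbalanced order: "TMS will be administered to the other site over a subsequent two-week period following a three week wash out period".

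The primary analysis in section 7.4 is a "Site x Time ANOVA on the Hamilton Depression rating scale comparing pretreatment to symptoms immediately following each round of stimulation". The Study Summary says the same in other words: "Clinical outcome will be evaluated on symptom scales in a TMS target x Time ANOVA". Neither place names a period, sequence or participant term, and no other section does.

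Three places bear on what the factors mean:

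- Section 7 (Statistical Plan) says the sample is adequate to "compare treatment sites relative to one another, since all patients will receive the standard targeting for TMS and also fMRI-guided TMS". That describes a within-patient comparison.
- Section 7.4.2 lists three time points: "comparisons between clinical symptoms at baseline, after the first 2-week treatment period, and at the end of the second 2-week treatment period".
- Section 7.4 adds "a Site x Time ANOVA for pre-treatment compared with the 6 month timepoint", intended to explore how well benefit is maintained. By then every patient has received both targets.

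On numbers, section 7 enrols 80 "to ensure that there are 40 patients who complete the full protocol with usable data". Section 7.4.1 allows that, if baseline characteristics differ between the order groups, "randomization will be temporarily suspended to assign patients to one or other of the two groups".

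**The concern.** Guided against standard targeting is the trial's only primary comparison, and the stated model can be fitted in more than one way. With Site within-patient, an analyst could code Time as before/after or by visit. In a crossover this matters, because scores after round 2 may differ from scores after round 1 for reasons unrelated to site, such as remaining benefit from round 1 or a time trend. Coding by visit takes that shift out of the site comparison. Before/after coding leaves it in the error and, if the analysed patients are unevenly split by order, in the estimate as well. The choice should not be left until the data are in.

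**Working it through.** **The plan's own figure.** Section 7.3 gives g = 1.225, power 0.80 and p = 0.05, and concludes that at least 6 patients are needed. The paired normal formula gives ((1.960 + 0.842)/1.225)² = 5.23, so 6, which agrees. This is a before-after figure for one treatment. It supplies no site difference, within-patient correlation or shift between rounds, so those inputs below are assumptions.

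**What before/after coding tests.** With one shared baseline, the Site by Time interaction is (post-guided − baseline) − (post-standard − baseline) = post-guided − post-standard. The baseline cancels. The test is a paired t on the two post-round scores, with no period term.

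**Inputs.** N = 40 completers (section 7). Assumed: orders 20:20, score SD 1, correlation 0.5 between the two post-round scores, site difference 0.5 SD, two-sided 0.05. The SD of the paired difference is √(1 + 1 − 2 × 0.5) = 1.

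**Model.** D = site difference ± shift + error, with the sign set by order. With no period term:

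- at equal orders the variance of D is 1 + shift², and the estimate is unbiased;
- at n1:n2 the bias is shift × (n1 − n2)/N.

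**Power at 20:20 (simulation).**

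| Shift (SD) | No period term | Period term |
|---|---|---|
| 0 | 87% | 87% |
| 0.25 | 86% | 87% |
| 0.5 | 81% | 87% |
| 0.75 | 73% | 87% |

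With no true site difference, the test without a period term rejects 2.8% of the time at a 0.5 SD shift, so it is conservative.

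**Bias at a 0.5 SD shift.**

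- 22:18: 0.5 × 4/40 = 0.05 SD, null rejection 3.6%
- 24:16: 0.5 × 8/40 = 0.10 SD, null rejection 6.3%
- 26:14: 0.5 × 12/40 = 0.15 SD, null rejection 11.0%

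With a period term the bias is 0 and the rejection rate 5.0%. The bias can run in either direction, depending on which order is over-represented.

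**How likely such splits are.** The documents do not give the number randomised. If patients are randomised equally to the two orders and 40 complete at random, a 24:16 split or worse has probability 0.117 with 80 randomised, 0.054 with 60 and 0.011 with 50.

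**Carryover as the source of the shift.** Suppose a share c of the round-1 gain adds in full to round 2, with site gains a and b and d = a − b. The two orders then have mean differences d − ca and d + cb, which average d(1 − c/2). Gains were set at 1.725 and 1.225 SD, or 1.1 and 0.6 SD.

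- c = 0: 87% with or without the period term.
- c = 0.25: 73% (larger gains) or 76% (smaller) without it, 77% with it.
- c = 0.5: 45% or 57% without it, 64% with it.

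The fall from 87% to 77% and 64% is the (1 − c/2) shrinkage, which a period term does not cure. If residual benefit does not add (the round-2 level is the larger of the new gain and the residual), there is no loss up to about c = 0.54 with the smaller gains or 0.7 with the larger. The period term then adds about 1 to 2 points at c = 0.9 to 1.

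**Visit coding.** With Site within-patient and Time coded by the three visits in section 7.4.2, the post-round-1 against post-round-2 level of Time is the period effect. In one simulated 24:16 data set with a 1 SD shift, a mixed model with site and visit gave 0.612, identical to the period-adjusted estimate. Without visit it gave 0.397.

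**The case against.** The strongest reply is that section 7.4.2 already lists three time points and section 7.4 speaks of each round. An analyst who codes Time that way has the period effect in the model. This stands. A reader might infer that the planned analysis omits period, or that its site estimate is biased. The documents do not support that: they leave the coding open, and the harm follows from only one of the codings.

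A second reply is that counterbalancing and the three-week washout deal with the shift. Counterbalancing removes bias at equal orders but does not prevent the power loss. The washout may keep the shift small, and nothing in the documents says how small. The c = 0.5 case is severe: with the larger gains it puts total improvement after round 2 at 1.225 + 0.5 × 1.725 = 2.1 SD or 1.725 + 0.5 × 1.225 = 2.3 SD. It also borrows 1.225 from a percentage-improvement effect at a different brain area.

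Third, marked imbalance is remote. Section 7 counts screen failures among the 80, so fewer than 80 are likely to be randomised. This also stands.

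A reader might also infer that Site means the order group, because section 7.4.1 compares two groups and only order is left to compare at 6 months. On that reading the order by visit interaction has 2 df and about 80% power against 87% for a 1-df contrast, with no carryover, the larger gains and a baseline correlation of 0.5. For the primary test the support is thin. The Study Summary names the factor as TMS target, section 5.4 separates order from site, section 7.4.1 concerns baseline checks, and the 6-month analysis is exploratory. It remains a secondary possibility.

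**Conclusion.** The point holds as a specification gap. Section 7.4 does not fix whether Site is within-patient, how Time is coded, or which contrast is the primary site test. On the better-supported within-patient reading, collapsing Time to before/after costs about 6 points of power at a 0.5 SD shift (81% against 87%) and 14 at 0.75 SD (73% against 87%). Unequal orders then add a bias of shift × (n1 − n2)/N. Coding Time by visit avoids both.

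The direction follows from algebra. The size rests on an assumed shift, correlation and site difference. With carryover of 0 to 25% of the round-1 gain, the period term recovers 0 to 4 points. Bias large enough to inflate type I error also needs an unlikely split. This is worth correcting because it is nearly free; it does not show that the trial's analysis is invalid.

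**What to change.** In section 7.4:

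- State that Site is a within-patient factor.
- Name the primary model: a linear mixed model with site and period (visit) as fixed effects and a random participant effect, using all available post-round scores. Section 7.5 already allows completed time points to be used.
- Name the 1-df site effect as the primary test.
- Keep the pretreatment score, either as a visit level or in a separate before-after test, so that the comparison with pretreatment is not lost.
- Say what Site means in the 6-month ANOVA, where every patient has had both targets.
- Acknowledge that the period term does not remove carryover proportional to each site's gain.

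A round-1-only comparison by first site (about 34% power under the inputs above) and a change-from-pre-round-2 analysis are optional sensitivity analyses. The latter needs the primary scale to be part of the short assessment before the first round-2 session, which section 6.2.2 does not say.

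The cost is SAP wording, with no new visits. With no shift, the standard error with a period term is 0.5 × √(1/n1 + 1/n2), against 1/√40 = 0.158 without. At 20:20 the two are equal and no power is lost. At 24:16 it is 0.161, and power falls from 86.9% to 85.5%, about 1.4 points.
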